### **Potential Harms/Risks and Inconveniences:**

There is a potential risk of/for the following (protections or mitigating strategies for each are presented in the next section):

- 1) Loss of confidentiality and privacy by participating in the study
- 2) irritation from the cutaneous mechanical and pressure sensitivity using the von Frey monofilaments, tuning fork, and Medoc pressure system. In our pilot study, women did not report adverse pain pressure from the von Frey monofilaments or the Medoc system.
- 3) Irritation of oral mucosa with collection of buccal cell swab sample. In our pilot study, women did not report any pain or irritation with buccal cell swab sample collection.
- 4) Irritation, pain, infection, bruising at the site, and fainting associated with venipuncture.
- 5) Participant burden and inconvenience with the research team contacting the participant with bi-weekly texting, providing educational videos, and weekly assessment measures
- 6) Eye strain with prolonged period of time looking at the computer/text screen
- 7) Risks related to BF and infant health outcomes.
- 8) Risks related to COVID-19 transmission.
- 9) Risks to the research team against biohazards.

### **Protection against Risk**

**1) Protection against disclosure of participants' privacy.** To minimize the risk of accidental disclosure of participants' private information and to maintain the confidentiality of their data, we will use the data management established during our pilot study and within the School of Nursing P20 Center for Accelerating Precision Pain Self-Management. Participant names will be masked by assigning each a unique participant identifier number (PID#) composed of random numbers (*i.e.*, the *code*). All sources and written data will be stored in a secured, locked PI study-designated office in [name]'s office at Hartford Hospital and [name] office at UConn Health. No source or written data will be stored at UConn Storrs School of Nursing. No identifiable information on participants will be retained at other study sites and the key to the *code* will be retained at UConn Storrs. Audio files coded with subject ID, will be uploaded on the day of the interview to UConn Onedrive and then deleted from the audio recorder. UConn Onedrive is HIPPA compliant with 2FA (2 factor authentication). A study team member will open up a Microsoft 365 word document in One Drive. Microsoft 365 word version has a transcription feature under voice. A member of the research staff will upload the .wav file into the word document and select transcribe. The transcribe feature converts speech to a text transcript with each speaker individually separated. A member of the team will listen to the audio file to make corrections on the transcript and edit the transcript. The member of the research team will save the file on One drive for additional analysis. The audio files on Onedrive will be deleted after the transcription has been completed and the study has closed. Only members of the research team has access to the files. The analysis of the transcription will be conducted in a qualitative analysis program, Taguette. Taguette is a web based freeware that will be downloaded onto UConn or HH laptops and computers. Each deidentified transcript will be uploaded into the program. The team will tag sections of each interview that reflect an idea or theme. These coded interview sections will then be collected across interviews to clearly describe an idea. These quotes will be used to answer the questions we are asking. The key to the *code* will be destroyed at the time of study closure with the IRB, and de-identified data and samples will be kept indefinitely. Electronic data will be stored on firewall-protected servers with access via computers that are password-protected and kept in locked buildings. Access to research data will be made available only to the investigators, and on an as needed basis to others on the research team. Information obtained as part of the study will remain confidential and not be disclosed to anyone (besides the participant) who is unaffiliated with UConn without consent from the participant, except as required by law or regulation. No information will be used in subsequent publications that would identify individual subjects.

**2) Protection against risk related to *cutaneous pain testing equipment*.** There is a minimal risk associated with the quantitative sensory testing component of this protocol. Some women may not

tolerate the mechanical pressure of the quantitative sensory testing. The quantitative sensory testing mechanical pressure stimulator's controller is equipped with an emergency shut-down feature, which will be engaged if the stimulator's pressure is more than women can tolerate. The participant will always be free to move away from the stimulus or to stop testing at any time. The device and these types of stimuli have been widely used within our group and in groups around the world for many years with no adverse events. In our pilot study, all participants completed the sensory testing. In our pilot we found women how responded to mechanical stimulation was predictive of pain sensitivity. There is minimal risk associated with mechanical sensitivity measurement via punctate probes. The punctate filaments have a blunt tip that allows them to indent the skin without causing a puncture. Further, there is a finite amount of force that can be applied with any one filament. We will assess vibration detection via a tuning fork. This instrument has minimal to no chance of causing injury. The fork will be set to vibrate and the blunt base of the fork will be placed against the skin surface.

**3) Protection against risk related to buccal cell swab samples.** There is minimal risk associated with buccal swab sample collection causing irritation of the mucosa. Women will be instructed to rinse their mouth with clean water to minimize bacterial contamination and decrease risk for irritation and infection from oral flora, before rolling the sterile buccal brush firmly on the inside of the cheek (10 times). The likelihood that these problems will occur is low.

**4) Protection against risk related to venipuncture for blood samples.** There is a minimal risk associated with blood draws which include irritation, pain, infection, bruising at the site, and fainting. Only experienced hospital or research staff will draw blood and no more than 2 attempts will be made to obtain blood.

**5) Protection against risk of symptoms of maternal well-being distress.** All participants will receive a pamphlet for the Hartford Hospital affiliated Institute of Living Peripartum Mood Disorder group, Postpartum Support International and suicide hotlines in their hospital discharge packet. Research team members at baseline will be trained to identify participants who exhibit emotional distress and will contact the PI for further questioning and consideration of referral to a mental health professional or social worker before hospital discharge if necessary. Secondly, the research team will check weekly for the Edinburgh Postnatal Depression Scale scores. A score  $>10$  will trigger a texted script to the participant to ask how they are doing, inform them of their concerning score, ask them if they need a referral or follow up with their health care provider. If the participant is unresponsive to text, the PI will follow up with a phone call and immediate referral, if required. If the participant's response includes thinking about suicide, it will trigger an immediate notification to [name], which includes reporting suicide risk to the health care provider (stated in the consent), assisting participant to immediate assessment at an urgent care or emergency department. In our pilot study, out of the 60 women one participant sought treatment for depressive symptoms. The pilot study found that all the women we contacted responded positively to the text and phone call follow-up and appreciated the support and referral for additional support. Likewise, this protocol surveillance addresses the needs of women during the fourth trimester and aligns with the CDC *Hear Her* campaign.

**6) Potential risk for participant burden and inconvenience.** Based on our pilot study results, women reported the baseline data collection to be burdensome. We addressed this risk by removing several questionnaires to decrease participant burden and recruiting during the prenatal period. We anticipate by recruiting women during the prenatal period, women will be prepared for the time for participation and decrease the time burden. Women in the pilot study, reported that completing the paper BF diary 6 times a day was burdensome. For this project, we are using a text-based daily (one entry) BF diary. Women did not report the weekly measurements via UConn Health REDCap as burdensome and that the bi-weekly texting contact was supportive without burdening them to travel to face-to-face visits and places the mother-infant dyad at risk for illness, such as COVID-19. The initial data collection

appointment will take approximately 45-60 minutes. The daily breastfeeding log will take 5 minutes/1 times a day for the first three weeks and from 15 days to 6 weeks a weekly breastfeeding log for 5 minutes a day. The scheduled data collection at Weeks 1, 2, 3, 9, 12, and 18 will take 30 mins to complete. The scheduled data collection for Weeks 6 and 24 will take 60 minutes. Additionally, participants may find logging daily feeding behaviors and multiple questionnaires an inconvenience. Receiving regular texts about their breast-feeding status may also be inconvenient. However, there is evidence to show that support via email and text during the first few weeks of delivery can be beneficial to breast feeding behaviors.

**7) Potential risk for eye strain with prolonged period of time looking at the computer/text screen.** We will instruct participants to use a low light setting and the use of anti-glare software to reduce the strain. Participants will also receive reminders and daily surveys to complete, which may be inconvenient. The time commitment is explained in detail in the consent and will be verbally explained to each subject prior to signing the informed consent. Additionally, we will limit reminders to texts and text pushes via REDCap related to missing data and scheduling 6 week and 6-month research visits, with follow up phone calls as needed to encourage completion, or phone calls to address emergent clinical concerns to decrease the inconvenience to the participant.

**8) Protection of risks related to BF and infant health outcomes.** Infants who BF or formula feed <6 times a day are at risk for dehydration and inadequate calorie intake. Women in the *BSM* intervention group will record daily number of feedings in their daily BF journal. Women in the attention control group will record the number of feedings per day once a week. A record of <6 feedings over a 24-hour period will trigger a notification email via UConn Health REDCap to the research team. The research nurse will contact the participant, evaluate the situation, and decide on the need for referral to a lactation specialist or their healthcare provider. This will also be done on a case-by-case basis. In our pilot study, no participants were referred for inadequate daily feedings. If the participant indicates they are having any difficulty such as mastitis or extreme pain, they will always be told to contact their PCP. Participants at every step of the research study will be encouraged to contact their provider if they are experiencing severe pain or discomfort such as fever.

**9) Protection of risks related to COVID-19 transmission.** Research team members will practice COVID-19 prevention measures at all points of face-to-face contact which include antenatal clinic, inpatient postpartum unit, follow-up data collection at 6 and 24 weeks at the Ambulatory Women's Health Services clinic, Hartford Hospital Lactation clinic, the School of Nursing BBL at UConn Health or UConn Health Outpatient Obstetrics/Gynecology Clinic. These measures will minimize personal density, allow distances, wear personal protective equipment and follow best practice consistent with CDC guidelines, state guidelines, and applicable University and hospital policies. In addition, the study design delivers standardized and best practice BF and BNP problem-solving skills during an acute period of pain when the rate of BF cessation is the highest via mobile technology and when face-to-face visits are most burdensome and places the mother-infant dyad at risk for illness, such as COVID-19.

**10) Protection of research team against biohazards.** All research teams will complete Biohazard and Transportation of Biohazard training through UConn Environmental Safety Department. Collection, or Hartford Hospital Health Stream, storage and assays of biohazardous samples will be performed in accordance with established safety guidelines and regulatory requirements.

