**For EACH Participant Population Describe Screening Procedures, if applicable**

The proposed RCT will be conducted to test the effect of the *BSM* intervention vs. an attention control group on BNP, BF exclusivity and duration, BF self-efficacy and maternal well-being to 24 weeks (Figure 4). Participants at baseline will complete assessments, quantitative sensory testing, and provide buccal cell and/or blood samples for assessment of select pain sensitivity SNPs and DNA methylation and again at 6 and 24 weeks at our research sites. At 1, 2, 3-, 9-, 12-, and 18-weeks participants will complete assessments via smartphone text and the UConn Health Research Electronic Data Capture (UConn REDCap) links, <https://health.uconn.edu/clinical-researchcenter/> when women shelter at home. If a participant does not have a smartphone, the study will provide a smartphone for them to receive texts and text links. All participants will receive educational material regarding infant development and age-appropriate play at 4, 8, 12, 16, 20, and 24 weeks to maintain contact and sustain engagement in the study. Following UConn Institutional Review Board approval, all recruitment and initial data collection will occur in collaboration with our clinical partners, at the UConn Health Center, a 234-bed tertiary care academic hospital delivering 700 infants a year with 560 women initiating BF; the Women Ambulatory Services at Hartford Hospital (HH), delivering 1000 infants a year with 800 women of diversity initiating BF (see letters of support) and women receiving private obstetric care at Hartford Hospital, delivering 2900 infants a year with 2320 initiating BF.

Prior to launch of the study, all research personnel will receive training on human subjects' research, HIPAA, and biological safety, handling and transportation. The study designated graduate assistants will develop a study binder of all protocols and each role will be established so that appropriate blinding procedures can be maintained throughout the study duration. [name] and the project manager will train all research personnel (graduate assistants, research assistants, and peer counselors) on the standardized intervention, scripts, protocols for women who need referrals or follow-ups for BF support or maternal well-being, documentation of schedule data collection visits, and establish weekly research team meetings.

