1	Days 1-5	Intervention Group ONLY: BL: 1 entry/ day Texts 2 times/ week breastfeeding coaching with links to Breastfeeding Modules 1-3 Maternal/Infant Care Modules 1-2	Personal computer/ smartphone	5 mins per entry  10 mins/ module	
	Days 1-5	Control Group ONLY: Texts 2 times/ week with links to Maternal/Infant Care Modules 1-2	Personal computer/ smartphone	10 mins/ module	
	Day 5	Both Groups: BB, PIS, MWB Control Group only: BL	Personal computer/ smartphone	10 mins	\$25 UConn Greenphire Gift Card or ecard
2	Days 8-12	Intervention Group ONLY: BL: 1 entry/ day Texts 2 times/ week breastfeeding coaching with links to Breastfeeding Modules 4-6 Maternal/Infant Care Modules 3-4	Personal computer/ smartphone	5 mins per entry  10mins/ module	
	Days 8-12	Control Group ONLY: Texts 2 times/ week with links to Maternal/Infant Care Modules 3-4	Personal computer/ smartphone	10 mins/ module	
	Day 12	Both Groups: BB, PIS, MWB Control Group only: BL	Personal computer/ smartphone	10 mins	\$25 UConn Greenphire Gift Card or ecard
3	Days 15-19	Intervention Group ONLY: BL: 1 entry/ day	Personal computer/	5 mins per entry	

		Texts 2 times/ week breastfeeding coaching with links to Breastfeeding Modules 7-9 Maternal/Infant Care Modules 5-6	smartphone	10mins/ module	
	Days 15-19	Control Group ONLY: Texts 2 times/ week with links to Maternal/Infant Care Modules 5-6	Personal computer/ smartphone	10 mins/ module	
	Day 19	Both Groups: BB, PIS, MWB Control Group only: BL	Personal computer/ smartphone	10 mins	\$25 UConn Greenphire Gift Card or ecard
Weeks 4-6	Days 21-40	Intervention Group ONLY: BL: 1 entry/ day Texts 2 times/ week breastfeeding coaching with links to Maternal/Infant Care Modules 7-12	Personal computer/ smartphone	5 mins per entry 5 mins/ module	
	Days 21-40	Control Group ONLY: Texts 2 times/ week with links to Maternal/Infant Care Modules 7-12	Personal computer/ smartphone	5 mins per entry	
Week 4	Day 26	Both Groups Infant development and play modules at 4 weeks	Personal computer/ smartphone	10 mins	

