Week 6	Day 40	Both Groups: 
 
• Buccal cell swabs and/or blood collection (15 ml or 3 teaspoons)
 
• QST
 
• BL
 
• BB, PIS, MWB
 
• Audio taped semi-structured interview: Reflection on participating in the study and the impact on their breastfeeding outcomes
 
	Clinic, smartphone	60 mins  15 mins	\$50 UConn Greenphire Gift Card or ecard
Week 8	Day 54	Both Groups Infant development and play modules at 8 weeks	Personal computer/ smartphone	10 mins	
Week 9	Day 61	Both Groups: BB, PIS, MWB, BL	Personal computer/ smartphone	10 mins	\$35 UConn Greenphire Gift Card or ecard
Week 12	Day 82	Both Groups: BB, PIS, MWB, BL Infant development and play modules at 12 weeks	Personal computer/ smartphone	10 mins	\$35 UConn Greenphire Gift Card or ecard
Week 16	Day 110	Both Groups Infant development and play modules at 16 weeks	Personal computer/ smartphone	10 mins	
Week 18	Day 122	Both Groups: BB, PIS, MWB, BL	Personal computer/ smartphone	10 mins	\$35 UConn Greenphire Gift Card or ecard
Week 20	Day 138	Both Groups Infant development and play modules	Personal computer/	10 mins	

		at 20 weeks	smartphone		
Week 24	Day 166	
Both Groups:
 
 
• Buccal cell swabs and/or blood (15 ml or 3 teaspoons) collection
 
• QST
 
• BL, BB, PIS, MWB
 
• Audio taped semi-structured interview: Reflection on participating in the study and the impact on their breastfeeding outcomes
 
• Infant development and play modules at 24 weeks
 
	
Clinic, Interview, smartphone
	
60 mins 15 mins
	\$75 + \$25 bonus UConn Greenphire Gift Card or ecard

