### Procedures and Data Collection at each Time Point.

At baseline we will collect demographic information, pain and coping scales, BF measures, maternal well-being symptoms, pain, BF and maternal self-efficacy scales, and quality of life health status.

Subsequently, quantitative sensory testing will be performed on the non-dominant forearm and a buccal cell and/or blood samples will be obtained for analysis of selected pain sensitivity SNPs and DNA methylation. All buccal cell swabs and/or blood (15 ml or 3 teaspoons) samples will be labeled with the participants' identification number. Blood will be kept at room temperature on the clinical unit and during transport, and buccal swabs will be stored in a freezer on the clinical unit at -20 degrees Fahrenheit, until transported to the SON Biobehavioral Lab (BBL) for processing and storage.

Study questionnaires will be administered via electronic surveys using UConn Health REDCap v11. Participant will access the UConn Health REDCap link before discharge to access and view texts, web links, and the video modules on either handheld device (e.g., smartphone, iPad) or computer desktop/laptop. All participants will receive an encrypted text (via UConn Health REDCap with an embedded link from Twilio) or an email per their preference with the study measures via UConn Health REDCap v11. After the initial surveys are completed, participants will be asked to contact a member of the research team to register their Greenphire incentive card. A member of the research team will complete the Greenphire form which includes social security number (field is encrypted), address, email and phone number to initiate the first incentive payment. The PROMPT study does not retain participant's social security number or address in our records. If the participant does not have a social security number, ecards will be provided by UConn School of Nursing business office. The team member will also refer the participant to WAHS and Outpatient Lactation scheduler or the UConn Health scheduler for the 6 week follow up visit.

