### IFSMT Proximal Outcomes.

#### Individual & Family Self-Management Behaviors.

**Acute BNP.** A visual analogue scale (0 - 100) used to measure BNP intensity during the last BF. Acute BNP will be measured with the short version of the Brief Pain Inventory. The Inventory has good reliability and validity with BNP. The Inventory has two subscales: pain intensity (4 items) and pain interference (7 items) and collects data on use of analgesics and of non-pharmacological measures. For initial data analysis, the average pain intensity and interference scores will be used, and other measures will be quantified. The McGill Pain Questionnaire short form is a reliable self-report measure of pain perception. It entails 15 verbal descriptors of sensory and affective dimensions of pain and is scored on a 4-point scale (0-none to 3-severe). Higher scores indicate higher levels of sensory and affective components of pain (range 0-45). Internal consistency reliability is in the excellent range for total pain score (Cronbach's alpha = 0.96).

**Cumulative BNP.** A score of acute BNP pain intensity from the VAS (0 - 100) at baseline, 1, 2, 3, 6, 9, 18, and 24 weeks will incrementally (baseline + 1 week, baseline + 1 and 2 weeks, etc.) be added together.

**NINR PROMIS Scales for Maternal Well-Being Symptoms.** The PROMIS scales of anxiety, perceived stress scale, sleep and fatigue. All PROMIS measures are based on the T-score (mean = 50, standard deviation = 10). In most cases 50 equals the mean in the U.S. general population.

**Edinburgh Postnatal Depression Scale.** Postnatal clinical screening tool for depressive symptoms with any score >10 indicates risk for depression and scores > 13 a depressive illness that requires referral. Women will be referred to their provider for fourth trimester care and may continue in the study. The scale has a sensitivity of 85%, specificity of 77% to identify women at high-risk for depression.

**H&H Lactation Survey.** A 20-item questionnaire maternal perception of milk supply with a 7-point Likert scale from 1 (strongly disagree) to 7 (strongly agree). Total scores ranged 20 ~ 140, with higher scores representing a higher perceived milk supply. The satiety subscale correlates with insufficient milk supply.

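### EPDS scores are read on a weekly check, so a score above 10 can wait up to 7 days to be seen; a REDCap alert on submission would remove that wait for review

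*Combined protocol and SAP*

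**What the plan says.** Under Protection against Risk, item 5, "the research team will check weekly for the Edinburgh Postnatal Depression Scale scores". A score above 10 leads to a scripted text; if the woman does not answer, the PI telephones and refers if needed. The item then adds: "If the participant's response includes thinking about suicide, it will trigger an immediate notification to" a recipient whose name is masked in this text. No day for the check and no time limit for the text are stated.

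The description of the scale under Individual & Family Self-Management Behaviors sets a second level, "scores > 13 a depressive illness that requires referral". Item 5 gives women at that level no separate or quicker route.

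The EPDS is an electronic form: "Study questionnaires will be administered via electronic surveys using UConn Health REDCap v11". It belongs to the maternal well-being battery in Table 1, and the measures table schedules it at all nine time points. Six of these are remote: "At 1, 2, 3-, 9-, 12-, and 18-weeks participants will complete assessments via smartphone text" and linked REDCap surveys.

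Item 8 of the same safety section handles low feed counts differently: "A record of <6 feedings over a 24-hour period will trigger a notification email via UConn Health REDCap to the research team". A research nurse then contacts the woman.

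**The concern.** The issue is when a score is seen, not where the threshold lies. A depression screen protects a participant only once somebody reads it. Here the stated rule for reading it is a weekly check, although the form is already in a system that the protocol uses to send alerts. Table 1 places the breastfeeding log and the well-being battery in the same assessments at weeks 9, 12 and 18. So a low feed count is described as alerting the team by itself, while a score needing referral waits for the weekly check. The text gives no reason for the difference.

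What is at stake is the timeliness of follow-up for women with depressive symptoms, in both groups. Sample size, power and the planned comparisons are not involved.

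**Working it through.** The plan states no figure for this delay, so there is none to reproduce.

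**1. Wait until a score is seen.** Input: one check per week (Protection against Risk, item 5), so the cycle is 7 days.
- Minimum: 0 days (form submitted just before the check).
- Maximum: 7 days (form submitted just after it).
- Mean: 7 / 2 = 3.5 days, assuming that forms arrive evenly over the week.
- With an alert on submission: about 0 days. Staff time from alert to contact comes on top and is not stated, either for the EPDS or for the feeding alert.

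**2. Is a faster reading described elsewhere?**

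| Place | What it provides | Reads EPDS scores sooner? |
|---|---|---|
| Data Safety Monitoring | Day-to-day oversight by PI and staff; after-hours contact details; weekly data checks | Not stated |
| Data Analysis and Management; Data Management | Real-time checks for missing data; weekly summary and review | Not stated |
| Protection against Risk, item 7 | Calls for emergent clinical concerns | Not stated |
| Protection against Risk, item 5 | Pamphlet with support group and hotlines | No; the woman must call |
| Screening Procedures; Design, Procedures, Materials and Methods | Staff training on referral protocols for maternal well-being; study binder | Content not in this text |

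**3. Where the wait may matter more.** Of the 9 EPDS time points, baseline and weeks 6 and 24 are in person, and weeks 1, 2 and 3 fall within the twice-weekly texting. Table 1 shows the last texting block, "Texts 2 times/ week with links to Maternal/Infant Care Modules 7-12" in the control group, ending on day 40, with coaching texts in the BSM group over the same days. That leaves weeks 9, 12 and 18: 3 / 9 = 33% of time points. Their Table 1 days are 61, 82 and 122, so they fall 61 − 40 = 21, 82 − 40 = 42 and 122 − 40 = 82 days after the texts end. Later entries such as "Infant development and play modules at 16 weeks" deliver content. Staff contact at weeks 9, 12 and 18 is as needed, for completion or, in the BSM group, breastfeeding concerns (Intervention Administration).

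**4. Suicidal thoughts.** The immediate notification depends on the participant's 'response'. The sentence follows the scripted text and the call for non-responders, so it may mean her reply to that text. But the protocol also uses the word for survey answers (Waiver or Alteration of Consent). If it covers survey answers, the described wait is 0 days. If it covers only text replies, a survey answer could wait up to 7 days.

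**5. Alert workload.** Forms: at most 280 × 9 = 2,520. Period: October 2021 to December 2024 is about 169.6 weeks, plus 24 weeks of follow-up = 193.6 weeks. 2,520 / 193.6 = 13.0 forms a week. The documents give no rate of scores above 10. With an assumed 5% to 20%, this is 13.0 × 0.05 = 0.65 to 13.0 × 0.20 = 2.6 alerts a week.

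**The case against.** The strongest reply is that the visible text may understate practice. The protocol mentions a separate referral protocol for maternal well-being, held with other procedures in a study binder, and alert routing could sit there. Item 5 also says that a score above 10 triggers the text, the same verb that item 8 uses for the REDCap email, so an automated text is conceivable. This limits the certainty. It does not displace the one explicit rule, a weekly check; if practice is faster, one sentence would settle the matter.

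It is also fair that a score above 10 indicates only risk, that women with a history of significant mental health disorder are excluded, and that 1 of 60 pilot women sought treatment for depressive symptoms. Infant dehydration is a more acute hazard, and control women record feedings only once a week, so the feeding alert is a model for the mechanism rather than a standard the EPDS breaches.

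The emphasis on weeks 9, 12 and 18 is open to challenge, because the twice-weekly texts are not described as reading EPDS scores either, and in the control group they are module links. It stands only as a judgement about other chances for distress to surface.

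A reader might infer that all data review is weekly. It is not: day-to-day oversight, real-time missing-data checks and the feeding alert are all described. A reader might also take the long gaps from weeks 9, 12 and 18 to the next visit as the delay. They are not, since the weekly check ends the wait within 7 days.

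**Conclusion.** The point holds as a modest participant-safety improvement. As written, a score above 10, including one above 13, can wait 0 to 7 days to be seen. This rests on reading the weekly check literally; the 3.5-day mean also needs even arrival of forms. No count of affected women can be given.

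Two stronger conclusions are tempting and are not supported. One is that suicidal survey answers are delayed: the protocol specifies immediate notification, and its wording only leaves open whether survey answers are covered. The other is that an alert would remove all delay before contact: it removes the wait for review, and staff response time remains unstated.

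**What to change.** - Add a REDCap alert on EPDS submission at every time point: to the research team for a total above 10, and to the recipient of the item 5 suicide notification for any answer indicating suicidal thoughts.
- State in item 5 that 'response' includes survey answers as well as text replies.
- Name the role that acts on alerts between weekly checks.
- Keep the weekly check as a back-up that every alert has been closed.

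The cost is one alert on an existing electronic form and a short wording change. The downside is that existing staff must handle alerts between weekly checks, as they already do for low feed counts; the participant-initiated contact line does not by itself provide that cover. At the assumed rates this is fewer than three alerts a week. Each such score already requires the scripted text, so the alert changes when the text is sent, not how many are sent. It applies equally to both groups.
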